9.3 VARIABLES

9.3.1 Exposures

Patient disposition will be provided according to post-stroke treatment (i.e. dabigatran, VKA, factor Xa inhibitors and no OAC therapy). Index event is defined as the acute ischemic stroke that led to hospital admission for eligible patients (baseline visit).

Dabigatran treated patients will be further stratified by newly diagnosed NVAf or prevalent NVAf, prior treatment with anticoagulation including type of anticoagulation therapy (dabigatran, VKA, Factor Xa Inhibitors, no anticoagulation) stroke severity measured by NIHSS score, dose of dabigatran, and timing of dabigatran treatment initiation.

We will describe the timing of dabigatran treatment initiation for secondary prevention of stroke within 3 months after index event in the post-stroke setting. Timing of dabigatran treatment initiation will be summarized as a continuous variable as well as a categorical variable (see [section 9.3.2.1](#)). For patients with dabigatran treatment initiated 28 days or more after index event, further analysis maybe carried out to determine their characteristics. These analyses will be detailed in a separate statistical analysis plan (see [Appendix 4](#)).

9.3.2 Outcomes

9.3.2.1 Primary outcomes

- The time lapsed from the index event to the initiation of the dabigatran treatment. This will be further categorized in specified time periods.

The following time periods will be considered, but could be revised (e.g. merging categories) depending on sample size 0-24h, >24-72h, >3-7d >7-14d, >14-28d, >28d-3m.

9.3.2.2 Secondary outcomes

- Description of baseline characteristics for patients treated with dabigatran according to time of dabigatran initiation.
- Description of self-reported factors important for physician's decision when to initiate dabigatran in the post-ischemic stroke setting for prevention of stroke and safety in NVAf.
- Description of self-reported factors important for physician's decision which dabigatran dose is used in the post-ischemic stroke setting for secondary prevention of stroke and safety in NVAf.

Definitions

Ischemic stroke is defined as an event characterised by sudden onset of acute focal neurological deficit (e.g. resulting in an impairment of speech, motor function, cognition, gazes, vision, and/or neglect) presumed to be caused by cerebral ischemia/infarction after exclusion of haemorrhage by imaging scans.

The index event is the date of first ever ischemic stroke.

The 3 month follow-up data point for patients is 90 (+/- 10) days after the index event.

Major intracranial haemorrhage is defined as symptomatic intracranial bleeding at any time after start of dabigatran treatment and within 3 months from index event.

The evaluation of intracranial haemorrhage will be done using the available CT/MRI scan after start of dabigatran treatment and within 3 months from index event.

Major extracranial haemorrhage is derived from safety documentation in the SITS registry.

Death is defined as all cause death.

9.3.3 Covariates

Patient characteristics such as age, stroke severity,(according to NIHSS) comorbidities, CHADS₂, CHA₂DS₂-VAS_c) and bleeding (HAS-BLED) risk scores (see [appendices 1-3](#)), prior oral anticoagulation treatment (dabigatran, Factor Xa Inhibitors, VKA, no OAC therapy), are regarded as potential covariates.

Patient characteristics will be assessed at index stroke date.

9.4 DATA SOURCES

SITS – International Stroke Treatment Registry (ISTR)

Data from the SITS-International AF registry will be extracted for the purpose of analysis. The SITS-International registry is an ongoing, prospective, internet-based, academic-driven, multinational, stroke register. All centres registering patients in the SITS registry are required to accept the basic rules of participating in registry: consecutive registration of all patients with stroke symptoms receiving alteplase (if the centre registers only patients treated with intravenous thrombolysis), irrespective of whether treatment was on- or off-label. If the centre registers all stroke patients in the registry, consecutive registration of all patients with

Protocol for observational studies based on existing data**BI Study Number 1160-0235****c03412460-01**

Proprietary confidential information © 2017 Boehringer Ingelheim International GmbH or one or more of its affiliated companies

stroke symptoms is obligatory. Death is collected separately in the SITS registry; however it is linked to the other outcomes at the 3 month time point from the index event. Register data has some inherent limitations. One of the most important limitations is we do not have any regular monitoring for source data verification, although monitoring was done during the period when the Safe Implementation of Thrombolysis in Stroke-Monitoring Study (SITS-MOST) was done [P07-00880]. In 2011-12, Karolinska Trial Alliance performed an independent monitoring of some selected Swedish centres and verified that data entered in the registry from these centres are accurate. Moreover, it is important to note that all results published based on SITS data with regard to baseline and demographic characteristics and outcome are comparable to other published data from randomised trials, registry data and centre data. SITS registry has a logical automatic validation system, which prevents the entry of erroneous or impossible data in the registry, to some extent. Regular checking of online report and prompt action by contacting centre is also a part of the work for SITS International Coordination members. Moreover, data are downloaded and cleaned regularly for scientific publications.

The SITS registry has implemented extended data entry for AF and oral anticoagulation since June 2014.

Specification of data collection from the index stroke event

At baseline: Demographic data, NIHSS and pre-stroke mRS, blood pressure, laboratory values (plasma glucose, cholesterol, coagulation status, liver function, kidney function,) medical history including comorbidities and concomitant medication, results of imaging scans, CHADS₂, CHA₂DS₂-VASc and bleeding risk by HAS-BLED scores.

At 24 hours: NIHSS score, blood pressure, laboratory and imaging scans if performed.

During hospital stay: details of concomitant medications, additional imaging scans prior to start of dabigatran treatment, any start/stop/change dabigatran treatment any results of the imaging scans

At 7 day or discharge if occurred earlier than 7 days: Date/time discharge, NIHSS scores, blood pressure, type of stroke and AF, medications

SITS is an academic-driven, non-profit, international collaboration. It is an initiative by the medical profession aimed at driving excellence in acute and secondary stroke treatment, and to develop new knowledge and leading research.

9.5 STUDY SIZE

Approximately 1000 NVAf patients who are treated with dabigatran etexilate within 3 months of index event constitute the main analysis population.

In order to address the further objective on characterisation of NVAf, the analysis population will be broadened to include all European patients with NVAf aged ≥ 18 presenting with their first acute ischemic stroke, regardless of subsequent oral anticoagulation use within the time period until approximately 1000 dabigatran patients are registered in SITS-AF.

Protocol for observational studies based on existing data**BI Study Number 1160-0235****c03412460-01**

Proprietary confidential information © 2017 Boehringer Ingelheim International GmbH or one or more of its affiliated companies

Data will be extracted from the SITS-AF registry from the European dataset for retrospective analysis. The number of patients included in the study is not driven by a formal sample size calculation but rather by available patient numbers, only descriptive or exploratory analyses will be performed for this study.

9.6 DATA MANAGEMENT

Data in the SITS registry are entered on-line through the SITS website.

Each investigator/study nurse has a personal access code which must be kept secret and used only by the owner. All data entry from a centre can be made by each member of the local team, but once the data entry is confirmed (i.e., cannot be changed), the person who made the confirmation will be identified on the data entry form.

For the purpose of analysis, a download will be made in Excel/ CSV format which will then be transferred in the appropriate advance data analysis software such as STATISTICA/ SAS.

9.7 DATA ANALYSIS

Descriptive statistics (absolute and relative frequencies, means, standard deviations, medians, inter quartile ranges, minimum and maximum values, 95% confidence intervals and proportions, as appropriate) for baseline and demographic characteristics for all included patients will be provided.

For the baseline characteristics we will calculate percentage proportions by dividing the number of events by the total number of patients, excluding missing or unknown cases as we generally did for all previous SITS-MOST and/or SITS-ISTR publications [[P07-00880](#), [P08-11746](#)].

In the separate statistical analysis plan further sensitivity analyses may be added (see [Appendix 4](#)).

9.7.1 Main analysis

The main analysis will focus on NVAF patients presenting with first ischemic acute stroke and treated with dabigatran within 3 months of index event:

For patients initiated on dabigatran within 3 months of index event, the time to dabigatran treatment initiation will be summarized as a continuous variable as well as categorical; the following time periods will be considered, but could be revised (e.g. merging categories) depending on sample size 0-24h, >24-72h, >3-7d >7-14d, >14-28d, >28d-3m.

There will be a descriptive analysis of self-reported factors important for physicians decision when to initiate dabigatran and which dose in the post-ischemic stroke setting for prevention of stroke and safety in NVAF. This analysis will be done overall as well as by timing and by dose of dabigatran, respectively.

Protocol for observational studies based on existing data**BI Study Number 1160-0235****c03412460-01**

Proprietary confidential information © 2017 Boehringer Ingelheim International GmbH or one or more of its affiliated companies

In addition, baseline and demographic characteristics will be presented stratified by timing and dose of dabigatran as well as by newly diagnosed NVAf or prevalent NVAf, prior treatment with anticoagulation including type of anticoagulation therapy, stroke severity measured by NIHSS score, if the sample size allows. Timing and dose of dabigatran treatment initiation will additionally be summarized for relevant baseline subgroups, e.g. based on stroke severity, if the sample size allows.

Protocol for observational studies based on existing data**BI Study Number 1160-0235****c03412460-01**

Proprietary confidential information © 2017 Boehringer Ingelheim International GmbH or one or more of its affiliated companies

9.7.3 Interim analysis

Not applicable.

9.8 QUALITY CONTROL

The automatic quality control of data is included in the SITS-Registry. This includes immediate feedback if data are missing, out of range data, illogical or potentially erroneous data. In addition to automatic quality control, regular online data monitoring is performed by SITS International Coordinating Office (ICO) members. All changes in the registry are automatically logged in the database

In addition to online data monitoring, raw data are downloaded every 6 months to check for inconsistency, completeness. Normally investigators are informed by newsletter regarding the completeness of data entry for overall registry and asked to complete the missing data. In case of major inconsistency or high rate of missing data investigators are contacted personally by e-mail.

9.9 LIMITATIONS OF THE RESEARCH METHODS**Non-interventional study based on existing data**

The quality of a study based on existing data relies on accuracy of recorded data. Important data may not be available. In the absence of randomisation and blinding, it can be difficult to control for bias and confounders.

Selection bias

There is a risk of selection bias at the patient level. Sites might preferentially include "interesting" cases to the SITS study. To minimize selection bias at the patient level, centres were reminded by e-mail every 3 months that all consecutive patients from each site who meet entry criteria must be included in the SITS-Registry.

Lost to follow up

As with all observational studies a loss to follow up can occur. In this study this will affect the patients with a pre-planned follow up (patients initiating dabigatran within the 3 months after the index event). However, considering the short time period of the follow up and the lost to follow up at 3 months in the general SITS Registry being 20%, a similar percentage of lost to follow up is expected in this study as well.

Channeling bias

Protocol for observational studies based on existing data**BI Study Number 1160-0235****c03412460-01**

Proprietary confidential information © 2017 Boehringer Ingelheim International GmbH or one or more of its affiliated companies

Channeling bias can occur due to preferential prescribing in relation to different risks for the events of interest: e.g., if dabigatran would be more often prescribed to higher risk patients compared to other treatments,

In order to assess potential channeling bias patients not receiving dabigatran within 3 months of the index event will be assessed. For example, patients initiating VKAs, other NOACs or no oral anticoagulation therapy will be assessed according to important patient baseline characteristics (e.g. age, sex, comorbidities, stroke and bleeding risk scores, concomitant medications).

Confounding

As in any observational study, confounding may affect the estimation of association between variables and clinical outcome events of interest and statistical techniques such as adjustment for covariates, stratified analyses, matching, etc. can be used to correct for these. But as only major confounders for selected research questions can be captured, unmeasured confounding may remain.

Exploratory analyses

No formal power calculation has been done for this descriptive study and up to 1,000 patients with an index stroke are planned to be included. Follow-up is limited to three months after index stroke. Subgroup analyses, in particular those restricted to dabigatran patients, are only exploratory in nature. Exploratory analyses are usually not the definitive answer to the question at hand, but can be useful to define hypotheses to be tested in subsequent confirmatory studies.

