Data analysis:	
Descriptive statistics (absolute numbers and relative frequencies, means, standard deviations, medians, inter quartile ranges, minimum and maximum values, 95% confidence intervals and proportions, as appropriate) for baseline and demographic characteristics for all included patients will be provided as appropriate for the variable of interest.
 
The main analysis will focus on NVAF patients presenting with first ischemic acute stroke and treated with dabigatran within 3 months of index event.
 
We will describe the timing of dabigatran treatment initiation for secondary prevention of stroke when treatment is initiated within 3 months in the post-stroke setting.
 
We will summarize the self-reported factors (i.e. as collected in the Registry using a dedicated question) important for the physician's decision for the timing when to initiate dabigatran and the self-reported factors important for which dabigatran dose is used in the post-ischemic stroke setting for prevention of stroke. Descriptions will also be stratified according to time of dabigatran initiation if sample size allows.
 
Dabigatran patients will be described stratified by timing of dabigatran treatment initiation, newly diagnosed NVAF or prevalent NVAF, prior treatment with anticoagulation including type of anticoagulation therapy, stroke severity measured by
		

Protocol for observational studies based on existing data

BI Study Number 1160-0235

c03412460-01

Proprietary confidential information © 2017 Boehringer Ingelheim International GmbH or one or more of its affiliated companies

Name of company: Boehringer Ingelheim			
Name of finished medicinal product: Pradaxa			
Name of active ingredient: Dabigatran etexilate			
Protocol date: 05 July 2017	Study number: 1160-0235	Version/Revision: 1.0	Version/Revision date: N.A.
	NIHSS score, dose of dabigatran, if the sample size allows.		
	Individual patient safety related information will not be captured during this study. Thus, individual safety reporting is not applicable.		
Milestones:	Individual patient data are collected in the SITS-AF Registry since the presentation of 'Extended data entry option for atrial fibrillation and oral anticoagulant', 1 st July 2014. After approximately 1000 dabigatran treated patients from European Centres are registered in SITS-AF (expected by July 2018), the data will be extracted and a retrospective final analysis will be performed.		

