6. MILESTONES

Milestone	Planned Date
Start of study/data collection	17 July 2017
End of data collection	31 July 2018 (The time-point when approximately 1000 dabigatran treated patients with completed observation time are expected to be registered in the database and data extraction will be done for the analysis)
Registration in the EU PAS register	13 July 2017 (registration no. EUPAS 17165)
Final report of study results:	31 December 2018 (Considering that the observation time for 1000 dabigatran treated patients is completed by 31 July 2018.)

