9.2 SETTING

Patients with NVAF presenting with their first ever acute ischemic stroke who are registered in the SITS International Registry from 1 July 2014 until approximately 31 July 2018 will be included in the study.

Inclusion criteria

- Patients with non-valvular Atrial Fibrillation (NVAF)
- Patients presenting with their first acute ischemic stroke
- ≥ 18 years of age

Exclusion criteria

- Documentation that the patient was enrolled or is planned to be enrolled in an investigational clinical trial at the time of the onset of the index event and for the duration of the data collection

Protocol for observational studies based on existing data

BI Study Number 1160-0235

c03412460-01

Proprietary confidential information © 2017 Boehringer Ingelheim International GmbH or one or more of its affiliated companies

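### The cap of 1,000 index-stroke patients in protocol section 9.9 contradicts section 9.5, and the shared inclusion and extraction date cuts off some late dabigatran starts

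*Protocol*

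**What the plan says.** The protocol attaches a figure of about 1000 to three different sets of patients.

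- **Dabigatran patients registered.** Abstract, Milestones: "After approximately 1000 dabigatran treated patients from European Centres are registered in SITS-AF (expected by July 2018), the data will be extracted". Section 9.5 makes approximately 1000 patients treated with dabigatran within 3 months the main analysis population. It then widens the cohort to all eligible NVAF first strokes, "regardless of subsequent oral anticoagulation use within the time period until approximately 1000 dabigatran patients are registered in SITS-AF".
- **Dabigatran patients with completed observation.** Section 6 describes 31 July 2018 as the point when "approximately 1000 dabigatran treated patients with completed observation time are expected to be registered in the database", with extraction then. The final-report date rests on the same condition.
- **All index-stroke patients.** Section 9.9, Exploratory analyses: "up to 1,000 patients with an index stroke are planned to be included". The same paragraph treats analyses restricted to dabigatran patients as subgroup analyses.

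Three further statements bear on these figures. Section 9.9 (Lost to follow up) expects a loss in this study similar to "the lost to follow up at 3 months in the general SITS Registry being 20" per cent. Section 9.2 includes patients "registered in the SITS International Registry from 1 July 2014 until approximately 31 July 2018 will be included", and SAP section 4 repeats that window. The 3-month data point is 90 (+/- 10) days after the index event (protocol 9.3.2.2, SAP 3.1).

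**The concern.** A reader of section 9.9 would expect a whole cohort of at most 1,000, with dabigatran patients as a part of it. A reader of section 9.5 would expect about 1000 dabigatran patients inside a larger cohort. The difference matters for the channelling-bias description (9.9, 9.12), which needs VKA, factor Xa inhibitor and no-anticoagulant patients alongside the dabigatran group.

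The dates raise a separate issue that reaches the primary outcome. SAP Appendix 1 dates a start up to the discharge/7-day visit on that visit's form, but asks about a dabigatran prescription after discharge only on the 3-month form. If patients enter up to the day of extraction, the most recent ones can show early starts but have had no 3-month visit at which a later start could be recorded. They would not appear as missing; they would simply not be counted as dabigatran starters. SAP section 6.1 expects no missing initiation times and so would not reveal this. SAP section 5 acknowledges selection by death, second stroke and leaving care, but not truncation at the data cut.

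**Working it through.** The 1000 does not come from a sample-size formula (section 9.5 says so), so there is no calculation to reproduce. The checks below are for consistency.

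**1. Section 9.9 against section 9.5.** Total cohort = dabigatran + VKA + factor Xa inhibitor + no anticoagulant. If the total is at most 1000 and dabigatran is about 1000, the other three groups together are about 0. Yet sections 9.3.1, 9.9 and 9.12 plan to describe those groups. This needs no assumption. For scale only, since the documents give no dabigatran share: at assumed shares of 50%, 20% and 10%, 1000 dabigatran patients imply totals of 1000/0.5 = 2000, 1000/0.2 = 5000 and 1000/0.1 = 10000.

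**2. Registered against completed.** The result depends on what completed observation means.

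- 3-month data obtained: 1000 × (1 − 0.20) = 800. Conversely, 1000/0.80 = 1250 registrations would be needed for 1000 complete.
- Time elapsed only: the 20% does not apply. The window from 1 July 2014 to 31 July 2018 is 1492 days. Under uniform accrual (assumed), 90/1492 = 6.0% register too late to reach day 90, leaving about 940 of 1000.

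**3. End date and the primary distribution.**

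- 31 July 2018 minus 80, 90 and 100 days is 12 May, 2 May and 22 April 2018. Index strokes after 12 May cannot have a 3-month visit within its window before extraction. Only those up to 22 April have passed the whole window.
- Fraction affected under uniform accrual: f = 80/1492 = 5.4%, 90/1492 = 6.0%, 100/1492 = 6.7%.
- Let p be the true share of dabigatran starts that occur after discharge. In the worst case every such start in the last 100 days is missed. Observed share = (1 − f)p / (1 − fp), so the shift is f·p(1 − p)/(1 − fp).
- At f = 0.067 and p = 0.5: 0.067 × 0.25/0.9665 = 0.017. The observed share is 48.3% instead of 50%, a shift of about 1.7 points. This is essentially the maximum over p.
- At p = 0.2: 0.067 × 0.16/0.9866 = 0.011, about 1.1 points.
- For comparison, the 95% half-width of a 50% proportion with n = 1000 is 1.96 × √(0.25/1000) = 3.1 points.
- Sensitivity: if accrual rose linearly over the window, f at 100 days is 1 − (1392/1492)² = 0.130. The shift at p = 0.5 is then 0.130 × 0.25/0.935 = 0.035, about 3.5 points. The documents give no accrual pattern.

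**The case against.** The strongest reply is that section 9.5 is the operative section and is clear, that the sentence in 9.9 is loose wording in a limitations paragraph, and that no analysis uses its number. That limits the consequence but does not remove the contradiction.

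A reader might infer that the registered and completed figures are irreconcilable. The documents do not support that. No section caps dabigatran registrations at 1000, so more could be registered with 1000 complete. Completed observation time can mean elapsed time. The figures are also described as approximate and expected, and as driven by available numbers. The two counts need reconciling, but they are not proved incompatible.

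A reader might also infer that the primary analysis will have only about 750 to 800 patients, with the half-width widening from 3.1 to 3.5 points. That does not follow either. The main population is defined by a dabigatran start within 3 months, not by a completed 3-month form. A patient who started in hospital stays in after later loss to follow-up. A post-discharge starter who is lost is never counted among the 1000.

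On truncation, it can be said that the shift is small, that SAP section 5 already calls the findings hypothesis generating, and that the discharge form records a foreseen anticoagulant start date. The first two stand. A foreseen date is not an actual dabigatran start, so the third does not repair the outcome.

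**Conclusion.** The concern holds in three parts of unequal weight.

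- The cap in section 9.9 contradicts section 9.5 without any assumption and is wrong as written.
- The registered and completed counts are ambiguous. 1000 registered corresponds to about 800 or about 940 completed, depending on the meaning. The 800 rests on the protocol's 20% loss and the 940 on uniform accrual.
- Using one date for inclusion and extraction truncates post-discharge starts for the last 90 to 100 days of accrual and moves the primary timing distribution slightly earlier. The bound of about 1.7 points assumes uniform accrual and the loss of every post-discharge start in the last 100 days. Accrual concentrated late would enlarge it.

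The study is descriptive and has no power calculation, so no error rate is affected. The reason to act is that the truncation is avoidable and falls on the primary outcome.

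**What to change.** - **Section 9.9:** replace the cap with about 1000 dabigatran starters within an NVAF first-stroke cohort that has no upper limit.
- **Abstract, section 6 and section 9.5:** state whether the 1000 are registered patients, patients whose 3 months have elapsed, or patients with 3-month data obtained, and use one definition throughout. Do not write 750 to 800 as the size of the primary analysis.
- **Protocol 9.2 and SAP section 4:** restrict the analysis set to index strokes at least 100 days before data extraction (22 April 2018 for extraction on 31 July 2018).
- **SAP section 6:** report the number of patients with 3-month data beside every result on post-discharge starts. The date restriction does not address loss to follow-up, which can only be disclosed.

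The first two changes cost wording only. The restriction changes the analysis set: it removes about 6 to 7% of patients under uniform accrual (more if accrual rose over time), or else the data cut must move later to keep the number.
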